#### **10.2.3 Assessment at the confirmatory scans**

On the confirmatory scans, the patient will be classified as progression confirmed (with an overall response of iCPD), or as showing persistent unconfirmed progression (with an overall response of iUPD), or as showing disease stability or response (iSD/iPR/iCR according to iRECIST).

#### **10.2.4 Confirmation of progression**

Progression is considered confirmed, and the overall response will be iCPD, if ANY of the following occurs:

- Any of the factors that were the basis for the initial iUPD to show worsening
  - For target lesions, worsening is a further increase in the sum of diameters of  $\geq 5$  mm, compared to any prior iUPD time point.
  - For non-target lesions, worsening is any significant growth in lesions overall, compared to a prior iUPD time point; this does not have to meet the “unequivocal” standard of RECIST 1.1.
  - For new lesions, worsening is any of these:
    - An increase in the new lesion sum of diameters by  $\geq 5$  mm from a prior iUPD time point
    - Visible growth of new non-target lesions
    - The appearance of additional new lesions
- Any new factor appears that would have triggered disease progression by RECIST 1.1

#### **10.2.5 Persistent iUPD**

Progression is considered not confirmed, and the overall response remains iUPD, if:

- none of the progression-confirming factors identified above occurs, AND

- the target lesion sum of diameters (initial target lesions) remains above the initial disease progression threshold (by RECIST 1.1).

Additional scans for confirmation are to be scheduled 4 to 8 weeks from the scans on which iUPD is seen. This may correspond to the next visit in the original visit schedule. The assessment of the subsequent confirmation scan proceeds in an identical manner, with possible outcomes of iCPD, iUPD, and iSD/iPR/iCR.

#### **10.2.6 Resolution of iUPD**

Progression is considered not confirmed, and the overall response becomes iSD/iPR/iCR, if:

- none of the progression-confirming factors identified above occurs, AND
- the target lesion sum of diameters (initial target lesions) is not above the initial disease progression threshold.

The response is classified as iSD or iPR (depending on the sum of diameters of the target lesions), or iCR if all lesions resolve.

In this case, the initial iUPD is considered to be pseudoprogression, and the level of suspicion for progression is “reset”. This means that the next visit that shows radiographic progression, whenever it occurs, is again classified as iUPD by iRECIST, and the confirmation process is repeated before a response of iCPD can be assigned.

#### **10.2.7 Management following the confirmatory scan**

If repeat scans do not confirm disease progression per iRECIST, as assessed by the investigator, and the patient continues to be clinically stable, study interventions are to continue and the regular scan schedule is to be followed. If disease progression is confirmed, patients may be discontinued from study interventions.

Note: If a patient has iCPD and clinically meaningful, study interventions may be continued after consultation with the sponsor. In this case, if study interventions are continued, tumor imaging should continue to be performed following the intervals as outlined in section [8.1.1](#).

#### **10.2.8 Detection of progression at visits after pseudoprogression resolves**

After resolution of pseudoprogression (i.e., after iSD/iPR/iCR), another instance of progression (another iUPD) is indicated by any of the following events:

- Target lesions
  - Sum of diameters reaches the disease progression threshold ( $\geq 20\%$  and  $\geq 5$  mm increase from nadir) either for the first time or after resolution of previous pseudoprogression. The nadir is always the smallest sum of diameters seen during the entire trial, either before or after an instance of pseudoprogression.
- Non-target lesions
  - If non-target lesions have never shown unequivocal progression, their doing so for the first time results in iUPD.
  - If non-target lesions have shown previous unequivocal progression, and this progression has not resolved, iUPD results from any significant further growth of non-target lesions, taken as a whole.

---

- New lesions
  - New lesions appear for the first time
  - Additional new lesions appear
  - Previously identified new target lesions show an increase of  $\geq 5$  mm in the new lesion sum of diameters, from the nadir value of that sum
  - Previously identified non-target lesions show any significant growth

If any of the events above occur, the overall response for that visit is iUPD, and the iUPD evaluation process (see section 10.2.3) is repeated. Progression must be confirmed before iCPD can occur.

The decision process on the subsequent iUPD is identical to the iUPD confirmation process for the initial disease progression, with one exception, which can occur if new lesions had occurred at a prior instance of iUPD, had not resolved, then worsened (increase in size or number) leading to the second iUPD. If new lesion worsening has not resolved at the confirmatory scan, then iUPD cannot resolve to iSD or iPR. It will remain iUPD until either a decrease in the new lesion burden allows resolution to iSD or iPR, or until new or worsening causes of progression indicates iCPD.

Additional details about iRECIST are provided in the iRECIST publication.

---

### 10.3 Appendix 3: Abbreviations

Abbreviation	Term
ADA	Anti-drug antibody
AE	Adverse event
AESI	Adverse event of special interest
ALK	Anaplastic lymphoma kinase
ALT	Alanine transaminase
ASaT	All-subjects-as-treated
AST	Aspartate transaminase
BOR	Best overall response (according to RECIST 1.1)
CA	Competent authority
CBR	Clinical benefit rate (according to RECIST 1.1)
CD	Cluster of differentiation
CI	Confidence interval
CR	Complete response (according to RECIST 1.1)
CRA	Clinical research associate
CRO	Contract research organization
cSCC	Cutaneous squamous cell carcinoma
CT	Computed tomography
CTC	Circulating tumor cell
CTCAE	Common Terminology Criteria for Adverse Events
CTLA-4	Cytotoxic T lymphocyte-associated protein 4
dMMR	Mismatch repair deficient
DoR	Duration of response (according to RECIST 1.1)
DRESS	Drug rash with eosinophilia and systemic symptom
EC	Ethics committee
ECG	Electrocardiography
ECOG	Eastern Cooperative Oncology Group
eCRF	Electronic Case Report Form
EEA	European Economic Area
EGFR	Epidermal growth factor receptor
Fc	Fragment crystallizable
FDA	US Food and Drug Administration

---

Abbreviation	Term
FoxP3	Forkhead box P3
GCP	Good Clinical Practice
HBV	Hepatitis B
HCV	Hepatitis C
IB	Investigator's Brochure
iBOR	Best overall response (according to iRECIST)
iCBR	Clinical benefit rate (according to iRECIST)
ICF	Informed Consent Form
ICH	International Council for Harmonisation
iCPD	Confirmed progressive disease (according to iRECIST)
iCR	Complete response (according to iRECIST)
IDMC	Independent Data Monitoring Committee
iDoR	Duration of response (according to iRECIST)
IEC	Independent ethics committee
Ig	Immunoglobulin
IL	Interleukin
IL-2R	IL-2 receptor
IL-15R	IL-15 receptor
iORR	Objective response rate (according to iRECIST)
iPFS	Progression-free survival (according to iRECIST)
iPR	Partial response (according to iRECIST)
irAE	Immune-related adverse event
IRB	Institutional review board
iRECIST	Response Evaluation Criteria In Solid Tumors for immune-based therapeutics
iSD	Stable disease (according to iRECIST)
iTtR	Time to response (according to iRECIST)
iUPD	Unconfirmed progressive disease (according to iRECIST)
IV	Intravenous
JAK	Janus kinase
mAb	Monoclonal antibody
MAPK	Mitogen-activated protein kinase

---

Abbreviation	Term
mCRPC	Metastatic castration-resistant prostate cancer
MRI	Magnetic resonance imaging
MSI(-H)	Microsatellite instability(-high)
MUGA	Multigated acquisition scanning
NK	Natural killer
NSAID	Non-steroidal anti-inflammatory drug
NSCLC	Non-small cell lung cancer
ORR	Objective response rate (according to RECIST 1.1)
OS	Overall survival
PCWG3	Prostate Cancer Clinical Trials Working Group 3
PD	Pharmacodynamic(s)
PD-1	Programmed cell death protein 1
PD-L1	Programmed cell death ligand 1
PD-L2	Programmed cell death ligand 2
PFS	Progression-free survival (according to RECIST 1.1)
PI3K	Phosphatidylinositol-4,5-bisphosphate 3-kinase
PK	Pharmacokinetic(s)
PP	Per Protocol
PR	Partial response (according to RECIST 1.1)
PSA	Prostate-specific antigen
PT	Preferred term
Q1	25 th percentile
Q2W	Every 2 weeks
Q3	75 th percentile
Q3W	Every 3 weeks
RECIST 1.1	Response Evaluation Criteria In Solid Tumors version 1.1
SAE	Serious adverse event
SAP	Statistical Analysis Plan
SD	Stable disease (according to RECIST 1.1)
SHP-1	Tyrosine phosphatase
SHP-2	Tyrosine phosphatase
SJS	Stevens-Johnson syndrome

---

Abbreviation	Term
SOC	System organ class
STAT	Signal transducer and activator of transcription
T1DM	Type 1 diabetes mellitus
T3	Triiodothyronine
T4	Thyroxine
TEAE	Treatment-emergent adverse event
TEN	Toxic epidermal necrolysis
TMB	Tumor mutational burden
Treg	Regulatory T cell
TSH	Thyroid stimulating hormone
TtR	Time to response (according to RECIST 1.1)
ULN	Upper limit of normal
WOCBP	Woman of childbearing potential
ZAP70	Zeta-chain-associated protein kinase

*Abbreviations of commonly used weight, height, and volume measures are not listed above.*

## **10.4 Appendix 4: Protocol Amendment history**

The PROTOCOL AMENDMENT SUMMARY OF CHANGES for the current Protocol Amendment is located directly before the TABLE OF CONTENTS.

## 10.5 Appendix 5: Country-specific requirements/differences

Country	Section(s) in Protocol Amendment 1	Country-specific requirements/differences
Czech Republic (per country-specific amendment CZ-2 dated 28Apr2022)	1.3.1 Schedule of activities, nanrilkefusp alfa combined with pembrolizumab	“In case pembrolizumab needs to be discontinued, nanrilkefusp alfa treatment can continue until disease progression or unacceptable toxicity and the schedule of activities for patients receiving nanrilkefusp alfa combined with pembrolizumab will apply” was replaced with “In case pembrolizumab needs to be discontinued, nanrilkefusp alfa treatment will be discontinued as well.”
	7.1 Discontinuation of study intervention	“In case pembrolizumab needs to be discontinued, nanrilkefusp alfa treatment can continue until disease progression or unacceptable toxicity” was replaced with “In case pembrolizumab needs to be discontinued, nanrilkefusp alfa treatment will be discontinued as well.”
France (per country-specific amendment FR-2 dated 23Aug2022)	1.1 Synopsis, Study population; 1.2 Schema; 4.2 Scientific rationale for study design	“Advanced hepatocellular carcinoma after recurrence or failure of an immune checkpoint inhibitor” is not applicable
	1.1 Synopsis, Estimated sample size	“Advanced hepatocellular carcinoma: 55 patients” is not applicable
	1.1 Synopsis, Statistical considerations; 9.4 Interim analysis	“Indication 4 (advanced hepatocellular carcinoma): Benchmark ORR = 17%; minimal ORR = 25.3%; desired ORR = 33%” is not applicable
	5.1 Inclusion criteria, criterion 4	“Advanced hepatocellular carcinoma” is not applicable
	9.5 Sample size determination	“Indication 4 (advanced hepatocellular carcinoma): 55 patients” is not applicable

---

2.0 Change History

Version/Date	Change Log
0.1	Created as new
0.2	Updated per Sotio and SME review
0.3	Updated per Sotio review
0.4	Updated per SME review
0.5	Updated per Sotio and SME review
1.0	Updated for signature per Sotio feedback
1.1	Updated per MSD feedback
1.2	Amended SAP based on PA#1, addition of PK analyses and updates based on ADaM development findings and IDMC requests.
1.3	Updated per Sotio review
1.4	Updated per Sotio review
2.0	Prepared for signature

4.0 Purpose

The Statistical Analysis Plan (SAP) describes the statistical methods to be used during the reporting and analyses of data collected under SOTIO Biotech AG Protocol Amendment 1 SC104 final version dated 20 April 2023.

5.0 Scope

The SAP outlines the following:

- Study objectives
- Study design
- Study endpoints
- Applicable study definitions
- Statistical methods

6.0 Introduction

This SAP should be read in conjunction with the study protocol and case report forms (CRFs). This version of the plan has been developed using protocol amendment 1.0 dated 20 April 2023 and CRFs version 1.0 dated 28 February 2022. Any further changes to the protocol or CRFs may necessitate updates to the SAP.

The SAP will be finalized prior to database lock.

Each version of the SAP requires approval by the sponsor.

6.1 Changes from Protocol

The following changes to the protocol have been applied:

Endpoint of “Circulating tumor cell (CTC) count conversion from >5 to <5 cells per 7.5 mL of blood” for metastatic castration-resistant prostate cancer (mCRPC) only will be analyzed as a conversion from ≥ 5 to <5 cells per 7.5 mL of blood.

Endpoint of “Confirmed PSA decline of $\geq 50\%$ ” will not only evaluate the response at 6 months post-trial entry: all timepoints will be considered as per the schedule of assessments (Section 1.3.3 of Study Protocol).

Additional sensitivity analyses and exploratory endpoints:

As a sensitivity analysis for Best Overall Response (BOR) as per RECIST 1.1: BOR will also be performed as per Prostate Cancer Clinical Trials Working Group 3 (PCWG3)-modified RECIST 1.1 to study the effect of progressive disease in bone on the BOR, for patients with mCRPC.

As a sensitivity analysis to Clinical Benefit Rate (CBR) as per RECIST 1.1: CBR will also be performed for all patients in mCRPC – with both measurable and non-measurable disease – as per PCWG3-modified RECIST 1.1, to study the effect of progressive disease in bone on the CBR.

Other sensitivity analyses using All Subjects as Treated (ASaT) population on selected efficacy endpoints.

As per the EMA guideline on the evaluation of anticancer medicinal products in man, the endpoint PFS2 has been added as an exploratory endpoint.

Following Futility Analysis in August 2023, recruitment to the study was stopped. Exploratory Endpoints will no longer be analyzed.

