#### **9.3.4 Exploratory endpoint analysis**

- OS

OS is defined as the time from the first day of study treatment until the date of death and will be summarized using Kaplan-Meier estimates for each indication separately. Patients with missing data will be censored at the last time known to be alive.

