12.7.11 OS – Exploratory Analysis: Not to be reported

OS will be summarized using Kaplan-Meier estimates for each indication separately. Patients with missing data will be censored at the last time known to be alive. OS will be analyzed on the ASaT and Efficacy Populations.

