12.7.11.1 Duration of Follow-up – Exploratory Analysis: Not to be reported

A reverse Kaplan-Meier analysis will be performed on OS to estimate the median follow-up incorporating censoring rules and flipping event/censored events.

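### After the futility analysis the SAP suppresses the planned OS summary and its only estimate of follow-up, while Kaplan-Meier PFS and DoR are still reported

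*SAP*

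**What the plan says.** Protocol section 3 lists OS as an exploratory endpoint. Section 9.3.4 gives the analysis: "OS is defined as the time from the first day of study treatment until the date of death", and it "will be summarized using Kaplan-Meier estimates for each indication separately", with censoring at the last time known alive. Section 4.1.3 schedules survival contacts every 3 months in year 1 and every 6 months after that, until the end of the study.

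SAP section 6.1 states: "Following Futility Analysis in August 2023, recruitment to the study was stopped". The next sentence is "Exploratory Endpoints will no longer be analyzed". The SAP then keeps the methods but suppresses the output:

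- OS is defined in 10.13.13, and its analysis in the ASaT and efficacy populations sits under the heading "12.7.11 OS – Exploratory Analysis: Not to be reported".
- Follow-up sits under "12.7.11.1 Duration of Follow-up – Exploratory Analysis: Not to be reported", where the text reads "A reverse Kaplan-Meier analysis will be performed on OS to estimate the median follow-up incorporating censoring rules and flipping event/censored events".
- PFS2, which the SAP itself had added, carries the same label (10.13.14, 12.7.12).

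Kaplan-Meier summaries of DoR (12.7.4), PFS (12.7.6) and TtR (12.7.7) remain. So do a swimmer plot (12.7.2), a survival-status listing (12.8.5.5) and a summary of death reports (12.8.5.6). SAP 7.3 and 7.4 still list OS and the other exploratory items without qualification, and 12.11 says pharmacodynamic endpoints will be reported elsewhere.

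**The concern.** Two things are at stake.

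First, a survival summary that the protocol planned was removed after an efficacy result was known, and the only context given is that recruitment stopped. The futility rule in Protocol section 9.4 discontinues an indication. It does not say that endpoints fall away.

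Second, PFS and DoR medians will be reported from a trial whose recruitment was cut short, with no cohort-level statement of how long patients were followed. A reader cannot easily tell a mature median from one shaped by early censoring.

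The retained outputs do not replace OS. PFS is censored at the last non-progression scan before new anti-cancer therapy, and a death after more than one missed assessment is censored as well (SAP 12.7.6). Some deaths therefore never count as PFS events, whereas OS counts every death. Scans are read locally in an open-label trial (Protocol 8.1.1), and OS does not depend on that reading.

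**Working it through.** The plan sets no event count, precision or follow-up target for OS, PFS or DoR, so there is no figure to reproduce. The check is a comparison of sections, followed by an illustration.

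**1. What is kept and what is lost**

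| Item | Data or method present? | Cohort-level summary reported? |
|---|---|---|
| OS | Yes: contacts (Protocol 4.1.3), last-known-alive derivation (SAP 10.13.15), method (SAP 12.7.11) | No |
| Median follow-up | Yes: SAP 12.7.11.1 | No |
| PFS, DoR, TtR | Yes | Yes, Kaplan-Meier by indication |
| Individual follow-up | Swimmer plot, listings | Per patient only |
| Deaths | Death reports | Summarized; only the handling of causes is described |

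Two summaries in each of six indications gives 2 × 6 = 12 cohort-level results that are specified but not reported in each analysis population. Only the six OS summaries were planned in the protocol. Median follow-up appears only in the SAP.

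**2. Cohort sizes**

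The planned total is 50 + 57 + 57 + 55 + 51 + 50 = 320. The futility-stage numbers in SAP section 11 sum to 21 + 12 + 12 + 19 + 35 + 21 = 120. The documents do not give enrollment at the time of the stop, so these figures show only that cohorts may be small.

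**3. Why a follow-up figure matters (illustration; every input is assumed)**

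Take exponential survival with a true median of 10 months. Censoring is uniform over either 3 to 9 months or 12 to 24 months, with 1,000 simulated cohorts per row. Cohort sizes are taken from the futility stage.

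| n | Censoring window (months) | Chance the Kaplan-Meier median is reached | Typical reverse Kaplan-Meier follow-up (months) |
|---|---|---|---|
| 12 | 3–9 | 0.39 | 6.0 |
| 21 | 3–9 | 0.35 | 6.0 |
| 35 | 3–9 | 0.35 | 6.0 |
| 12 | 12–24 | 0.97 | 17.7 |
| 21 | 12–24 | 0.99 | 18.0 |
| 35 | 12–24 | 1.00 | 17.9 |

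The pattern follows from the survival function S(t) = 0.5^(t/10). S(9) = 0.5^0.9 = 0.54, so under short follow-up the curve crosses one half only by chance. S(12) = 0.5^1.2 = 0.44, so under long follow-up it nearly always crosses. Identical true survival gives different-looking reports, and the follow-up estimate shows which situation applies. The same logic holds for PFS and DoR.

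**4. Which follow-up measure fits**

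PFS and DoR are censored at tumor assessments. OS is censored at the last-known-alive date, which SAP 10.13.15 takes as the latest of many dates, tumor assessments among them. For a living patient censored on both endpoints, the OS censoring time is therefore never earlier than the PFS one. It is often later, because scans stop at progression or new therapy (Protocol 8.1.1.3) while survival contacts continue. Reverse Kaplan-Meier on OS can thus overstate the follow-up relevant to PFS and DoR. Reverse Kaplan-Meier on PFS uses the matching censoring. For DoR the censoring scheme matches, but the time origin is the first response.

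**The case against.** The strongest defense is that this is a declared reduction in scope after early termination. It appears under changes from protocol, in a SAP that section 6.0 says is to be final before database lock. It covers the exploratory tier as a class, including PFS2. Every primary and secondary efficacy endpoint stays, and those are where an inactive combination would show poorly. OS is exploratory, all analyses are descriptive, and no conclusion in the plan rests on it. With truncated cohorts, OS may be immature.

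Most of this stands, and it rules out some stronger readings a reader might be tempted to make:

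- **That OS was dropped selectively, or because the result was negative.** The documents show sequence, not motive, and the wording covers the whole tier. Its exact reach is unclear, because 12.11 keeps pharmacodynamic reporting elsewhere and 7.3 and 7.4 are unchanged, but that does not establish selection.
- **That no information on follow-up remains.** The swimmer plot, the survival-status listing, the death summary and the exposure summary (SAP 12.5.1) all remain. Only a summary estimate is missing.
- **That deaths will be shown without timing.** SAP 12.8.5.6 describes how causes are handled and does not exclude dates. SAP section 12.0 lists all collected data.

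The defense does not explain why stopping recruitment removes the need for a summary whose data are still collected and whose method is written. Immature OS is a reason to show follow-up beside the estimate. It is not a reason to omit both.

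**Conclusion.** The point holds as a disclosed, tier-wide but results-timed omission with no rationale beyond stopped recruitment. Its size is one exploratory protocol endpoint (OS) and one SAP-defined summary (median follow-up), each absent at cohort level in all six indications. No hypothesis test, primary analysis or secondary analysis changes, so this is a worthwhile improvement and not a flaw in the main result.

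The conclusion assumes that survival contacts continued as scheduled after recruitment stopped. The documents do not show how complete those data are. The SAP approval date is not in the available text, so the interval between the futility result and the change cannot be checked. That the change followed the result is clear from the wording of section 6.1.

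**What to change.** Before database lock:

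1. Remove the non-reporting label from SAP 10.13.13, 12.7.11 and 12.7.11.1, and amend the statement in 6.1 to exempt OS and follow-up.
2. Report descriptive Kaplan-Meier OS and reverse Kaplan-Meier median follow-up by indication, in the ASaT and efficacy populations that 12.7.11 already names for OS.
3. Add reverse Kaplan-Meier on PFS by indication, so that the follow-up shown with PFS and DoR reflects tumor-assessment censoring.
4. Align 7.3, 7.4 and 12.11 with whatever stays dropped, and state the reason in 6.1. Biomarker and PFS2 analyses can stay dropped.

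The cost is a few extra descriptive tables per cohort, largely from methods already written. The downside is wide intervals and possibly immature OS, which the follow-up estimate would itself make visible.

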7.0 Study Objectives and Endpoints

7.1 Primary Objective

- To estimate the antitumor efficacy of SOT101 in combination with pembrolizumab

